# 7 DISCONTINUATION OF STUDY INTERVENTION AND PARTICIPANT DISCONTINUATION/WITHDRAWAL

# 7.1 Discontinuation of Study Intervention

It may be necessary for a participant to permanently discontinue (definitive discontinuation) study intervention. Participants who discontinue study intervention early will have an early discontinuation visit as described in the SoA (Section 1.3). After the early discontinuation visit, participants will be encouraged to remain in the study for all remaining visits and study procedures as outlined in the SoA, with the exception of the urine pregnancy test, dispensation of study intervention and Instructions for Use, and PK sampling. Participants will be encouraged to have the biopsy at Week 48 as planned in the SoA. Participants who are unwilling or unable to wait until Week 48 will have the biopsy procedure as part of the early discontinuation visit if they have received study intervention for at least 36 weeks. Samples for clinical safety laboratory assessments, amylase and lipase, coagulation parameters, and calcitonin do not need to be collected at visits occurring more than 30 days after discontinuation of study intervention except as needed for lab abnormalities/AEs that require follow-up to resolution.

Note that discontinuation from study intervention is NOT the same thing as a withdrawal from the study.

An individual participant will not receive any further IP if any of the following occur:

- Withdrawal of consent/assent from further treatment with IP.
- Lost to follow-up.
- Noncompliance that, in the opinion of the investigator or sponsor, warrants withdrawal (eg, refusal to adhere to scheduled visits).
- Pregnancy in a female participant.
- An AE that, in the opinion of the investigator or the sponsor, contraindicates further dosing; specific examples include:
  - Clinically significant tachyarrhythmias, including but not limited to life-threatening arrhythmia, eg, sustained ventricular tachycardia or ventricular fibrillation.
  - Acute pancreatitis

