#### 9.4.1 General Considerations

The primary analyses will be of safety. No formal hypothesis testing will be performed. Treatments will be compared in tables using descriptive statistics.

Exploratory efficacy analyses will use nominal 2-sided 5% significance levels (equivalent to nominal 1-sided 2.5% significance levels) unless otherwise stated.

The primary estimand of interest for the histological endpoints will use the treatment policy strategy. The treatment policy approach applies to intercurrent events of treatment discontinuation, deviations from the protocol titration schedule, changes in background medication, liver events, or use of prohibited medication or other protocol deviations. The treatment policy strategy will also be used to handle the intercurrent events for continuous endpoints.

Participants will be analyzed according to their randomized IP assignment and dose, irrespective of the treatment they actually received. Analyses will be performed using the FAS and/or per protocol analysis sets, as appropriate (Table 14). The FAS will include all randomized and treated participants who received at least one dose of IP irrespective of their protocol adherence, addition or modification of background medications, discontinuation of study intervention or switches to alternative medications, and continued participation in the study.

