#### 3.3 General Considerations

The primary analyses will be of safety. No formal hypothesis testing will be performed. Treatments will be compared in tables using descriptive statistics.

Exploratory efficacy analyses will use nominal 2-sided 5% significance levels (equivalent to nominal 1-sided 2.5% significance levels) unless otherwise stated.

The primary estimand of interest for the histological endpoints will use the treatment policy strategy. The treatment policy approach applies to intercurrent events of treatment discontinuation, deviations from the protocol titration schedule, changes in background medication, liver events, or use of prohibited medication or other protocol deviations.

For efficacy analyses, participants will be analyzed according to their randomized investigational product (IP) assignment and dose, irrespective of the treatment they actually received. Analyses will be performed using the full analysis set (FAS) and/or per protocol (PP) analysis sets, as appropriate. The FAS will include all randomized and treated participants who received at least 1 dose of IP irrespective of their protocol adherence, addition, or modification of background medications, discontinuation of study intervention or switches to alternative medications, and continued participation in the study.

All statistical summaries and analyses will be performed using Statistical Analysis System (SAS®) software version 9.4 or above (SAS Institute, Cary, North Carolina, USA).

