# 3.3.1.2 Definition of On-study and On-treatment

All adverse events (AEs) with start date on or after the date of first treatment will be considered on-study. On-treatment AEs are those occurring within the on-study period and within + 7 days of treatment discontinuation. All AEs leading to discontinuation of IP will be considered on-treatment.

On-study assessments (eg, vital signs, clinical laboratory tests, ECG) are defined as those occurring after the date and time (if available) of administration of the first dose of IP. On-

treatment assessments are defined as those occurring within the on-study period and on or before the date of administration of the last dose of IP with the following windows following treatment discontinuation:

- Fasting plasma glucose (FPG): +1 day from treatment discontinuation.
- Biopsy, liver tests (alanine aminotransferase [ALT], aspartate aminotransferase [AST], total bilirubin [TBL], and alkaline phosphatase [ALP]), and disease-specific biomarkers: + 30 days from treatment discontinuation.
- All other efficacy and safety: +7 days from treatment discontinuation.

Assessments other than AEs recorded on the day of first treatment and with time unavailable for the assessment or for the first dose, will be considered to be not in the on-study/on-treatment periods. For listings of AEs, analysis phase will be indicated as on-treatment if the AE starts within the on-treatment period, as 'pre-treatment' if it starts prior to the on-treatment period, and as 'post-treatment' if it starts after the on-treatment period.

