## 4.2.3.4 Primary Analysis of Other Endpoints

Unless otherwise indicated, analyses of tertiary/exploratory histological endpoints and continuous exploratory endpoints at Week 48 will include both on- and off-treatment measurements while analyses of endpoints at multiple timepoints through Week 48 will only include on-treatment measurements. The treatment effect for binary exploratory endpoints will be analyzed by the Cochran-Mantel-Haenszel (CMH) test, stratified for T2DM presence and F2/F3 fibrosis stages. The difference in proportion (unstratified response difference) with Miettinen-Nurminen (ie, score-based; without stratification) 95% confidence interval, and nominal p-value from CMH chi-square test will be provided.

Continuous endpoints summarized for a single post-baseline timepoint (Week 48) will be analyzed using ANCOVA with baseline, baseline T2DM status, baseline fibrosis stage, and treatment as independent variables, using multiple imputation. If an issue is encountered for fitting an ANCOVA model (eg, collinearity with intercept), a simplified model may be used. For analysis of (absolute) change from baseline, endpoints will be analyzed without transformation and LSMEAN change from baseline by treatment; the treatment effect as the LSMD will be reported as point estimates and 95% confidence intervals with p-values provided for treatment effect. For analysis of percent change from baseline, ANCOVA will be performed using log-transformed values. Point estimates and 95% confidence intervals of percent change from baseline by treatment and ratio change from baseline will be reported with a nominal p-value for treatment effect (Section 4.2.3.2). Rubin's rules (Rubin 1987) will be used to pool LSMEAN and LSMD values and associated standard errors across multiply imputed datasets and will provide the reported estimates and p-values. The following variables will be log-transformed: ALT, AST, APRI, triglycerides, PRO-C3, FIB-4, FPG, (total and high molecular weight) adiponectin, and C-peptide. Other variables may be log-transformed if required.

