Change from baseline in continuous fibrosis scores from artificial intelligence, if available, will be analyzed by ANCOVA, as described above. Additionally, continuous scores from artificial intelligence for key histological features of NASH (inflammation, steatosis, ballooning), if available, may be analyzed using ANCOVA. Change from baseline in fibrosis stage (non-continuous scores) based on biopsy at Week 48 will not be analyzed by ANCOVA, but will instead be summarized descriptively by treatment using shift tables.

Analysis of continuous endpoints at multiple timepoints will be performed using MMRM adjusting for baseline value, fibrosis stage (F2/F3), T2DM status, analysis visit, treatment, the interaction of treatment and analysis visit and the interaction of baseline value and analysis visit. Only on-treatment data (Section 3.3.1) will be included in the model and missing data will not be imputed. An unstructured covariance structure will be used. If the computational algorithm fails to converge, the following structures will be tested in the following order:

Toeplitz, first-order autoregressive (AR[1]), and compound symmetry. Alternatively, covariates may be dropped from the model. Estimates, standard errors, and 95% confidence intervals of mean change from baseline or percent change from baseline will be reported by treatment and analysis visit. Restricted Maximum Likelihood estimation will be used in MMRM analyses.

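### The SAP's repeated-measures model uses on-treatment data only, although the protocol sets treatment policy for continuous endpoints; post-discontinuation HbA1c and SBP are dropped and the change is not declared

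*SAP*

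**What the plan says.** **Protocol.** Section 9.4.1, and the synopsis in the same terms, sets treatment policy for the histological endpoints, with treatment discontinuation first among the intercurrent events. It then adds: "The treatment policy strategy will also be used to handle the intercurrent events for continuous endpoints". Section 9.4.2 names ANCOVA with multiple imputation for change in HbA1c. Section 7.1 says that after stopping drug "participants will be encouraged to remain in the study for all remaining visits and study procedures as outlined in the SoA". The exceptions listed there do not include HbA1c or vital signs. Safety laboratory samples, which include ALT and AST, "do not need to be collected at visits occurring more than 30 days after discontinuation of study intervention".

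**SAP.** Section 3.3 carries over the histology statement, "The primary estimand of interest for the histological endpoints will use the treatment policy strategy", but not the sentence on continuous endpoints. Section 4.2.3.4 keeps both on- and off-treatment data for histology and for continuous endpoints analysed at Week 48 alone. For repeated timepoints it does the opposite: "analyses of endpoints at multiple timepoints through Week 48 will only include on-treatment measurements". It repeats the rule for the MMRM: "Only on-treatment data (Section 3.3.1) will be included in the model and missing data will not be imputed". Section 3.3.1.2 sets the on-treatment window. For liver tests, biopsy "and disease-specific biomarkers: + 30 days from treatment discontinuation"; for HbA1c and SBP the residual rule applies, "All other efficacy and safety: +7 days from treatment discontinuation". Section 4.2.3.5 lists no additional analyses. Section 2 declares the per protocol change and states that nothing else in the planned analyses differs from the protocol.

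**The concern.** Excluding measurements because the participant has stopped treatment is the reverse of treatment policy for that event. The on-treatment MMRM, which relies on data being missing at random after discontinuation, targets the effect that would be seen if everyone had stayed on drug. The protocol asks for the effect whether or not they stayed.

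Two consequences follow. First, if more participants stop on cotadutide than on placebo, the HbA1c and SBP effects would tend to look larger than under the protocol's estimand. Protocol 2.2.2 reports more nausea and vomiting on cotadutide in completed studies, so this direction is plausible, but it is not shown. Second, one report would present body weight under treatment policy and HbA1c under an unlabelled on-treatment estimand, while SAP 2 tells the reader that the analyses match the protocol.

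**Working it through.** The plan gives no figure on this point, so the check has three parts: which endpoints are affected, how many scheduled values are lost, and how far the two estimands could differ.

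**1. Endpoints affected.** SAP 4.2.3.4 does not list the MMRM endpoints, so the assignment is inferred from the endpoint definitions (SAP 4.2.3.1) and visit tables (SAP 3.3.2).

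- HbA1c: followed through Week 48, with three analysis visits (SAP Table 8). MMRM.
- SBP: followed through Week 48, with nine analysis visits to Week 48 (SAP Table 3). MMRM. The SAP amendment history entry on 4.5.4.2 also refers to an exploratory efficacy MMRM for vital signs.
- ALT and AST: followed through Week 48 with several visits (SAP Table 4). MMRM.
- Lipids: one scheduled post-baseline visit at Week 48, so they fit the single-timepoint ANCOVA.

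**2. Scheduled values lost.** Visit days come from Protocol Table 4: HbA1c on days 85, 169 and 337; SBP on days 29, 57, 85, 113, 141, 169, 225, 281 and 337. A value is dropped if visit day > last-dose day + 7.

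| Last dose | Cut-off day | HbA1c dropped | SBP dropped |
|---|---|---|---|
| Week 12 (day 85) | 85 + 7 = 92 | 169, 337: 2 of 3 | 113, 141, 169, 225, 281, 337: 6 of 9 |
| Week 24 (day 169) | 169 + 7 = 176 | 337: 1 of 3 | 225, 281, 337: 3 of 9 |

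An early-discontinuation value taken within 7 days of the last dose is kept. In both rows it falls in an analysis window that already holds a value: Week 12 for HbA1c is days 2–127 and for SBP days 71–98; Week 24 is days 128–253 and 155–196. The counts therefore stand.

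For ALT and AST, data are kept to last dose + 30 days, and samples are not required at visits more than 30 days after stopping. The number of required samples dropped is 0.

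**3. Difference between the estimands.** Let Δ be the on-treatment effect, d the share of the active arm that stops, and f the fraction of the effect lost after stopping. Placebo discontinuation is ignored and off-treatment follow-up is taken as complete.

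Treatment-policy effect = (1 − d)Δ + d(1 − f)Δ = (1 − df)Δ, so the ratio of on-treatment to treatment-policy effect is 1/(1 − df).

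| d | f = 25% | f = 50% | f = 100% |
|---|---|---|---|
| 10% | 1/0.975 = 1.03 | 1/0.95 = 1.05 | 1/0.90 = 1.11 |
| 20% | 1/0.95 = 1.05 | 1/0.90 = 1.11 | 1/0.80 = 1.25 |
| 30% | 1/0.925 = 1.08 | 1/0.85 = 1.18 | 1/0.70 = 1.43 |

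Both d and f are assumptions. With about 55 randomized 2:1:2:1, each dose has about 55 × 2/6 = 18 participants, so d = 20% is about 4 people per dose.

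**4. Declaration.** SAP 4.2.3.5 offers no treatment-policy counterpart. The vital-sign safety tables are also limited to on-treatment data (SAP 4.5.4.2), and HbA1c is not among the safety laboratory variables (SAP Table 10). Post-discontinuation HbA1c and SBP therefore enter no planned model, and SAP 2 does not mention it. For HbA1c there is a second undeclared difference: an MMRM without imputation in place of ANCOVA with multiple imputation.

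**The case against.** The strongest reply is that this is a documentation matter on exploratory endpoints in a discontinued programme. Safety is primary, p-values are nominal, and the SAP states its data rule openly, twice. It does follow treatment policy for the single-timepoint Week 48 endpoints, such as body weight, the FibroScan measures and most biomarkers. All of that is true and keeps the impact modest. It does not remove the contradiction with Protocol 9.4.1 or make the statement in SAP 2 correct.

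It can also be said that the protocol leaves detail to the SAP and that the ANCOVA sentence in Protocol 9.4.2 is partly out of date, since it still names absolute change in body weight, which version 3 removed as an endpoint. An MMRM for an endpoint followed over time is then a reasonable elaboration. That has force for the choice of model, and for ALT, AST and SBP Protocol 9.4.2 sets no method at all. But choosing a repeated-measures model does not require on-treatment data; an MMRM can include off-treatment values.

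Finally, the ratios are illustrative. Attendance after stopping is encouraged, not assured. The SAP's imputation model (4.2.3.3) conditions on arm, strata and baseline but not on discontinuation, so missing off-treatment values would be filled largely from participants who stayed on drug. The difference actually seen could be smaller than the table suggests. This stands, and is why the figures are given as a range under stated assumptions.

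**Conclusion.** The concern holds. For treatment discontinuation, the SAP's multiple-timepoint MMRM contradicts the protocol's strategy for continuous endpoints, and the change is not declared. The departure is confined to that event: data after titration deviations, background-medication changes or other listed events are kept while the participant is on treatment.

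Scheduled data are lost for HbA1c and SBP, in the amounts counted above for each participant who stops but stays. For ALT and AST the defect is mainly an unlabelled estimand. The inflation range of 1.03 to 1.43 rests wholly on assumed d and f, and 1.43 is an upper end that needs 30% discontinuation with the whole effect lost. The primary safety analyses and the histology analyses are unaffected. This should be fixed before analysis, though nothing primary depends on it.

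**What to change.** - **SAP 4.2.3.4:** make the main analysis of HbA1c and SBP use all on-study measurements regardless of discontinuation. For HbA1c at Week 48, use the protocol's ANCOVA with multiple imputation, or list the MMRM in SAP 2 as a change.
- **On-treatment MMRM:** keep it as a supplementary analysis, labelled as a hypothetical (on-treatment) estimand.
- **ALT and AST:** state that sampling is not required more than 30 days after stopping, so the analysis is essentially on-treatment, and label it so.
- **SAP 3.3 and SAP 2:** carry the protocol's sentence on continuous endpoints into 3.3, and correct the statement in SAP 2 that nothing else changed.
- **Minimum alternative:** keep the on-treatment MMRM as the main analysis, label its estimand, and list it in SAP 2 as a departure from Protocol 9.4.1 and 9.4.2.

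The cost is SAP wording and one extra model run for each of HbA1c and SBP, with no new data collection. The downside is that effects may look somewhat smaller, and off-treatment values that are still missing must be imputed or assumed missing at random.

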### 4.2.3.5 Additional Analyses of Other Endpoints

None

# 4.2.3.6 Subgroup Analyses

Analysis of the following tertiary/exploratory endpoints will be repeated for subgroups:

- Proportion of participants with resolution of NASH without worsening of liver fibrosis based on biopsy at Week 48
- Proportion of participants with improvement of liver fibrosis by at least 1 stage without worsening of NASH based on biopsy at Week 48

For each subgroup, 95% confidence intervals of the difference in proportions (response difference) will be computed using the method of Miettinen-Nurminen (ie, score-based; without stratification) as well as p-values for general association (chi-square test). Results will be presented as Forest plots as well as corresponding tables.

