# 9.2 Sample Size Determination

Approximately 7440 participants were originally planned to be screened/enrolled to achieve 1860 randomly assigned to study intervention, including 300 in Part A. However, this study has prematurely stopped randomization as the cotadutide program has been discontinued. The sample size for this study includes approximately 55 randomized participants. The original

sample size calculations for Part A are detailed below.

In Part A, 300 participants were originally to be randomized in a 2:1:2:1 ratio. Approximately 100 participants were planned for each for each dose of cotadutide and 50 participants for each matching placebo group. This sample size was derived with respect to the comparison of each cotadutide group to the pooled placebo group for the proportion of participants with resolution of NASH without worsening of liver fibrosis at Week 48. The sample size would provide > 90% power for the test of each dose versus placebo to detect a difference of 20% in NASH resolution assuming a placebo response rate of 15%. The calculations assumed a 2-sided alpha level of 0.05.

The effects were assumed after any impacts from treatment discontinuation, early withdrawal, missing data imputation, etc. The assumed effect sizes for the histology-based endpoints took into account the PROXYMO interim analysis results as well as the published effects for a GLP-1 receptor agonist (Newsome et al 2021).

Note: "Enrolled" means a participant's, or their legally acceptable representative's, agreement to participate in a clinical study following completion of the informed consent process. Potential participants who are screened for the purpose of determining eligibility for the study but are not randomly assigned/assigned in the study, are considered "screen failures."

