# 3.3.4 Multiplicity/Multiple Comparisons

No formal hypothesis testing will be performed, and all p-values are nominal. Therefore, no adjustments for multiplicity will be made.

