## Subgroups:

- Participants with and without T2DM at randomization (as-randomized strata)
- Fibrosis category (F2/F3) at randomization (as-randomized strata)

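### SAP 4.2.3.6 gives a p-value within each T2DM and F2/F3 level but no comparison between levels, so the subgroup display cannot show whether the effect differs by subgroup

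*SAP*

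**What the plan says.** SAP 4.2.3.6 repeats two binary histology endpoints in subgroups: NASH resolution without worsening of fibrosis, and fibrosis improvement without worsening of NASH. There are two factors with two levels each: "Participants with and without T2DM at randomization (as-randomized strata" and "Fibrosis category (F2/F3) at randomization (as-randomized strata". Each level gets a Miettinen-Nurminen 95% confidence interval for the response difference "as well as p-values for general association (chi-square test". On display: "Results will be presented as Forest plots as well as corresponding tables".

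On the status of these results, SAP 3.3 says "Exploratory efficacy analyses will use nominal 2-sided 5% significance levels" and SAP 3.3.4 says "No formal hypothesis testing will be performed, and all p-values are nominal".

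Nothing compares one level with the other. SAP 4.2.3.5 lists no additional analyses. The only interaction terms, in SAP 4.2.3.4, are treatment by visit and baseline by visit in the repeated-measures model. Protocol Section 9 describes no subgroup comparison, and neither document says how the subgroup p-values are to be read.

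**The concern.** A subgroup display by T2DM or fibrosis stage is normally read for one purpose: to see whether the treatment effect differs between levels. A p-value against placebo inside one level does not measure that. Whether it falls below 0.05 depends on the size of the level and on chance as well as on the effect. Two levels with the same true effect can fall on opposite sides of 0.05, and the plan supplies no number to show that the difference between them is compatible with zero.

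At stake is a misreading: a forest plot with one level below 0.05 and its complement above it suggests that cotadutide works only with (or only without) T2DM, or only in one fibrosis stage. Calling the p-values nominal deals with multiplicity. It does not turn a within-level p-value into a comparison between levels.

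**Working it through.** **Inputs from the documents.** Protocol 9.2: 15% placebo response and a 20-point difference, so 35% on cotadutide, stated for NASH resolution in the original design; two-sided 5%; 2:1:2:1 allocation; originally about 100 per dose and 50 + 50 placebo; now about 55 randomized. Protocol 4.1.1: each fibrosis stage was to be capped at about 70%.

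**Assumptions.** Each dose is compared with pooled placebo, as in the sample-size text; SAP 4.2.3.6 does not say so. The T2DM split is not given for this trial, so level splits from 50:50 to 70:30 are used. The true effect is the same in every level.

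**Step 1: reproduce the stated power.** Protocol 9.2 says "The sample size would provide > 90% power for the test of each dose versus placebo". With 100 per group and mean rate 0.25:

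power = Φ{[0.20 − 1.96·√(2·0.25·0.75/100)] / √[(0.15·0.85 + 0.35·0.65)/100]} = Φ{(0.20 − 0.120)/0.0596} = Φ(1.34) = 0.91.

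The stated figure is reproduced.

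**Step 2: current size.** 55 × 2/6 ≈ 18 per dose and 18 on pooled placebo. Exact power of one overall dose comparison is 27%.

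**Step 3: each level pair.** The levels are small, so the power of the uncorrected chi-square test was obtained by enumerating all binomial outcomes. The two levels of a factor share no participants and are independent. With level powers A and B: P(exactly one) = A(1−B) + B(1−A); P(neither) = (1−A)(1−B).

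| Per arm in each level | A, B | Exactly one | Both | Neither | Only one, given at least one |
|---|---|---|---|---|---|
| 9 + 9 | 0.158, 0.158 | 27% | 3% | 71% | 91% |
| 11 + 7 | 0.162, 0.089 | 22% | 1% | 76% | 94% |
| 13 + 5 | 0.215, 0.110 | 28% | 2% | 70% | 92% |

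Example, 11 + 7: 0.162 × 0.911 + 0.089 × 0.838 = 0.222. If the test is computed in its n−1 (CMH general association) form, the 9 + 9 row becomes 20% exactly one and 78% neither.

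**Step 4: the whole display.** Two doses and two factors give four level pairs per endpoint. At least one pair splits in about 58% of simulated trials. Two endpoints give eight pairs. Applying 15% versus 35% to both endpoints, with 60% T2DM and 55% F3, the figure is about 74% at a between-endpoint correlation of 0.5 (72-75% for correlations of 0.7 to 0.3). It is about 79% when level sizes vary at random.

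**Step 5: what a between-level contrast would give.** For the difference of two risk differences at 9 per arm per level:

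SE = √{2·[0.15·0.85/9 + 0.35·0.65/9]} = √0.0789 = 0.281; half-width 1.96 × 0.281 = 0.55.

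So the 95% interval is about ±55 points. A uniform effect would be flagged as different about 5% of the time per contrast. Power is 11% if the true effects differ by 20 points and 30% if they differ by 40.

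**The case against.** The strongest reply is that the plan already limits the harm. The primary analysis is safety, all efficacy is exploratory, every p-value is nominal, development has stopped, and each level is shown with its confidence interval. At about 9 per arm, those intervals show a careful reader how little the data can separate. Describing results by randomization stratum is also a legitimate use of subgroups. All of this stands and makes the point minor. It does not supply the missing comparison.

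The proposed contrast is itself weak: it is imprecise, its point estimate can be had by subtraction, and a wide interval covering zero could be misread as proof of a uniform effect. That is fair. It is why the contrast should be shown as an interval with an explicit caution and not used as a test.

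Three stronger readings are tempting, and the documents support none of them.

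- A reader might infer that a uniform effect will usually look confined to one subgroup. For a given dose and factor, the usual result is that neither level is significant. Even at the original 300, the one-level-only rate would be 45-54% across the splits examined.
- A reader might infer that the many p-values inflate the error rate several-fold. That sets the chance of at least one low p-value across the display against a per-test 5%. It is a multiplicity matter that SAP 3.3.4 openly declines to adjust for.
- A reader might infer that the sponsor plans to claim an effect in one level. Neither document says so.

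**Conclusion.** The gap is real: SAP 4.2.3.6 reports a statistic that cannot answer whether the effect differs by T2DM or fibrosis stage, and it omits the one that could. Under a uniform 15% versus 35% effect, about one level pair in four shows significance in one level only. Whenever any level is significant, it is nearly always the only one of its pair. The three-quarters figure for a split somewhere in the display is less secure than the per-pair figures. It needs comparisons per dose against pooled placebo, which the subgroup section does not state. It also needs the NASH-resolution rates to hold for the fibrosis endpoint, which the documents do not say. The level splits are assumed throughout. Severity is minor, because no efficacy conclusion of this trial is confirmatory.

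**What to change.** In SAP 4.2.3.6:

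- Delete the within-level chi-square p-values.
- Keep the response difference with its Miettinen-Nurminen 95% interval for each level.
- Add, for each factor and dose, the between-level difference in risk differences with its 95% interval, and name the interval method.
- State that no effect is claimed in a single level, and that a non-significant contrast is not evidence of homogeneity.
- Say which comparison the subgroup results use (each dose against pooled placebo, or otherwise).

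The cost is a short SAP edit and one extra column in the forest-plot tables, with no new data. The drawback is that the contrast will be very imprecise. Its width shows directly that about 55 participants cannot separate the subgroups.
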